### **19.0 Data and Safety Monitoring**

The Data and Safety Monitoring Board (DSMB) of The University of Michigan Comprehensive Cancer Center (UMCCC) is the DSMB for this study. This committee is responsible for the review and monitoring the study's scientific progress, accrual rate and any serious adverse events.

Each participating site is required to have its own Data and Safety Monitoring Committee (DSMC) for the study. This committee will be composed of the local site principal investigator, site co-investigator(s), site data manager or study coordinator and other members of the study staff involved in the conduct of the trial. During the committee's bimonthly meeting, the principal investigator will discuss matters related to:

- Enrollment rate relative to expectations, characteristics of participants
- Safety of study participants (Serious Adverse Event & Adverse Event reporting)
- Adherence to protocol (protocol deviations)
- Completeness, validity and integrity of study data
- Retention of study participants

These meetings are to be documented by the site data manager or study coordinator using the Protocol Specific Data and Safety Monitoring Report (DSMR), signed by the site principal investigator or co-investigator. Each site is required to submit the completed DSMR to the Multi-Site Coordinator at the University of Michigan Clinical Trials Office on a quarterly basis together with other pertinent documents.

Similarly, protocol deviations are to be documented using the Notice of Protocol Deviation Form and requires the signatures of both the sites data manager or study coordinator and the site principal investigator [or co-investigator]. These reports are to be sent to the University of Michigan Clinical Trials Office within 7 calendar days of awareness of the event and on a quarterly basis with the Protocol Specific Data and Safety Monitoring Report.

The Clinical Trials Office is responsible for collating all the Data and Safety Monitoring Reports from all the participating sites, and providing the information to the Data Safety Monitoring Board.

## **20.0 Clinical Monitoring Procedures**

Clinical studies coordinated by The University of Michigan Comprehensive Cancer Center (UMCCC) must be conducted in accordance with the ethical principles that are consistent with Good Clinical Practices (GCP) and in compliance with other applicable regulatory requirements.

This study will be monitored by a representative of the Clinical Trials Office (CTO) of the UMCCC. Monitoring visits will be made during the conduct of the study and at study close-out.

Prior to subject recruitment, a participating site will undergo site initiation meeting to be conducted by the Clinical Trials Office. This will be done as an actual site visit; teleconference, videoconference, or web-based meeting after the site has been given access to the study database and assembled a study reference binder. The site's principal investigator and his study staff should make every effort in attending the site initiation meeting. Study-related questions or issues identified during the site initiation meeting will be followed-up by the appropriate UMCCC personnel until they have been answered and resolved.

The first annual monitoring visit should occur after the first five study participants are enrolled or twelve months after a study opens, whichever occurs first. The initial annual visit is not justified unless there is at least one participant enrolled on a study. At a minimum, a routine monitoring visit will be done at least once every 12 months, or once during the course of the study if the study duration is less than 12 months. The purpose of these visits is to verify:

- Adherence to the protocol
- Completeness and accuracy of study data and samples collected
- Proper storage, dispensing and inventory of study medication
- Compliance with regulations

Monitoring visits may be in the form of a site visit or a review of the documents at the CTO. During a monitoring visit to a site, access to relevant hospital and clinical records must be given by the site investigator to the CTO representative conducting the monitoring visit to verify consistency of data collected on the CRFs with the original source data. While most patient cases will be selected from patients accrued since the previous monitoring visit, any patient case has the potential for review. At least one or more unannounced cases will be reviewed, if the total accruals warrant selection of unannounced cases.

The Clinical Trials Office expects the relevant investigational staff to be available to facilitate the conduct of the visit, that source documents are available at the time of the visit, and that a suitable environment will be provided for review of study-related documents. Any issues identified during these visits will be communicated to the site and are expected to be resolved by the site in a timely manner. For review of study-related documents at the CTO, the site will be required to ship or fax documents to be reviewed.

Participating site will also undergo a site close-out upon completion, termination or cancellation of a study to ensure fulfillment of study obligations during the conduct of the study, and that the site Investigator is aware of his/her ongoing responsibilities. In general, a site close-out is conducted during a site visit; however, site close-out can occur without a site visit if all of the following apply:

- No patient has signed the Informed Consent Form and has enrolled into the study
- Investigational agent has not been dispensed
- All investigational agent and materials have been returned as defined for the study or destroyed and accounted for properly.

## 20.1 Quality Assurance and Audits

The Data Safety Monitoring Board can request a ‘for cause’ audit of the trial if the board identifies a need for a more rigorous evaluation of study-related issues. A “for cause” audit would be conducted by the Quality Assurance Review Committee (QARC) of the University of Michigan Comprehensive Cancer Center.

A regulatory authority (e.g. FDA) may also wish to conduct an inspection of the study, during its conduct or even after its completion. If an inspection has been requested by a regulatory authority, the site investigator must immediately inform the Clinical Trials Office that such a request has been made.

## 21.0 Statistical Considerations

**21.1** General Description: This is a single-arm, Phase II trial to characterize the clinical outcome of standard of care, cetuximab concurrent with radiation, in a special population (head and neck cancer patients who cannot tolerate concurrent chemoradiotherapy due to advanced age, poor performance status or concurrent illness), and to determine if biomarker response to a loading dose of cetuximab is predictive of that outcome.

**21.2** Number of patients: Fifty evaluable patients will be accrued to the trial, which is expected to take 36 months. A patient will be evaluable for the primary objectives if he or she undergoes Research Biopsy #1 and #2 and either completes the full course of cetuximab+RT or has cetuximab+RT stopped for toxicity. Unevaluable patients will be replaced.

**21.3** Analysis plan

**21.3.1 Primary Objective 1:** Determine changes in tumor EGFR, pEGFR, downstream signaling and novel phosphoproteins following a loading dose of cetuximab in patients who are poor candidates for chemoradiation (age  $\geq 70$  years or with significant co-morbidities) and are therefore treated with cetuximab+radiation. These markers will be assessed in tumor biopsies harvested before and after the loading dose of cetuximab. The initial analysis will use descriptive and graphical statistics to determine if any of the markers require transformation prior to analysis. Markers may be assessed on a continuous, ordinal or

dichotomous scale; markers measured on a continuous scale will be analyzed via general linear models (possibly after transformation), while ordinal and dichotomous markers will be analyzed via cumulative logit and logistic regression analyses, respectively. The primary questions to be answered in this objective are: is the marker modulated by the loading dose of cetuximab; are there baseline clinical or demographic variables that are related to significant variation in biomarker response to the loading dose of cetuximab? For continuous variables, the null hypothesis that the mean value of the change (absolute or percent of baseline) equals zero will be tested by means of a single sample t-test. The second question will be answered by means of analysis of variance on baseline clinical and demographic variables. For dichotomous markers, patients will be stratified into elevated versus not elevated at baseline, and Wald tests on logistic regression parameter estimates will be used to test the null hypothesis that the proportion of patients changing state from baseline is different from 0.5, and to determine if any subset of patients defined by clinical or demographic factors have proportions significantly different from 0.5. Ordinal markers will be handled in a similar fashion.

[figure not shown]
21.3.2 **Primary Objective 2** Characterize clinical outcomes, including local recurrence, progression-free survival and overall survival in these patients, and correlate these clinical outcomes with the changes in tumor EGFR, pEGFR, downstream signaling, and novel phosphoproteins. Logistic regression and proportional hazards (Cox) regression will be used to relate clinical out (local recurrence, progression-free survival or overall survival) to changes in markers across the loading dose. All of the markers will be analyzed, but markers that are modulated by the loading dose (identified in Primary Objective 1) will be of particular interest.

21.3.3 **Primary Objective 3** *Describe the toxicity, in particular mucositis/dysphagia, of this regimen.* Adverse events will be tabulated by grade (NCI CTCAE v4), category (mucositis and dysphagia are expected to be the most common) and relatedness to treatment (not, unlikely, possibly, probably or definitely). The proportion of patients experiencing Grade 3 or worse adverse events at least possibly related to treatment will be calculated, accompanied by a 95% exact binomial confidence interval. Possible baseline demographic and clinical predictors of such toxicity may be evaluated by means of logistic regression, but, due to the low expected number of such toxicities, any such modeling will be strictly exploratory.

21.3.4 **Secondary Objective 1** *Conduct normal mucosa EGFR assessment for comparison with tumor sample.* The change in tumor EGFR level across treatment, relative to EGFR in normal mucosa, will be evaluated by means of repeated measures ANOVA.

21.3.5 **Secondary Objective 2** *Correlate HPV presence and titer with p53 status and clinical outcome.* HPV status ( $\pm$ ) will be added to the models of Primary Objective 2 to determine if +HPV patients respond to therapy differently than -HPV patients, but, due to the limited expected number of +HPV patients, such analyses will be considered exploratory.

**21.4 Justification of Design:** While radiation with concurrent cetuximab has become the standard of therapy in patients with locally advanced squamous cell head and neck carcinoma, the clinical outcome of the therapy have not been systematically studied. In addition, therapy with cetuximab is expensive, and, while less toxic than platinum-based therapies, is not without toxicity, and a screen for patients from whom cetuximab would be of benefit would be desirable. Therefore, all patients on this protocol are treated the same, and the primary objectives are focused on comparing patients who do respond to patients who do not. Because this is the standard of care, and these patients have no other treatment options, there is no provision for halting the trial due to low efficacy or excess toxicity (although therapy can, of course, be stopped in individual patients if clinically warranted). The sample size is justified in terms of Primary Objective 2, specifically relating change in a continuous marker to progression-free survival. Monte Carlo simulation was used to simulate the analysis of a single biomarker related to progression-free survival. It was assumed that 50 patients were accrued over 36 months, that the median survival was 22 months, the proportional hazards regression was performed six months after the last patients was treated, and that the biomarker was normally distributed. The power of the null hypothesis of no marker effect (tested at  $\alpha=0.05$ ) was assessed as the effect size of the marker (here, represented as the difference between the mean of the marker for patients with PFS less than the median versus the mean of the marker for patients with PFS greater than the median, divided by the standard deviation) was increased from 0 to 1.5 standard units. The result is shown in Figure 20.1, where it is seen that the power to reject the null hypothesis of no effect is at least 80% if the effect size is 1.1 standard units or greater, which would be considered a moderately large effect.

*Figure 20.1* Power of proportional hazards regression for a marker that discriminates between patients with greater than versus less than median progression-free survival.

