### 1.1 Study Hypothesis and Rationale

Bonner *et al* investigated the benefit of the addition of cetuximab to radiation. It was concluded that cetuximab improves locoregional control and reduces mortality without increasing the common toxic effects associated with radiotherapy to the head and neck. In our study, we propose to select locally advanced head and neck cancer patients, who are older than age 70 or are not deemed candidates for chemotherapy. This group was not extensively investigated in the earlier randomized trial, in that

---

 Abbreviations: **CR**, complete response; **EGFR**, epidermal growth factor receptor; **MAPK**, mitogen-activated protein kinase; **PI3K**, phosphatidylinositol 3-kinase; **PR**, partial response; **RT**, radiation treatment/therapy; **STAT**, signal transducer and activator of transcription; **TMA**, tissue microarray.

90% of patients in the Bonner study had a KPS of 80 or greater, and the median age of the patients was 57. The primary end-point of this trial is to characterize local progression free survival in these patients, when treated with cetuximab+radiation.

We also propose to develop a molecular pharmacodynamic predictor of local control after treatment with combination cetuximab-radiation. We hypothesize that tumor EGFR degradation and other markers of down-stream EGFR inhibition as well as novel phosphoproteomic markers observed in tumor biopsies taken 7 days after the administration of cetuximab, will predict the effectiveness of cetuximab-radiation. The first biopsy will be obtained prior to administration of the loading dose of cetuximab. Prior to initiation of cetuximab concurrent with radiation, on Day 7, following the cetuximab loading dose, a tumor biopsy for the biomarkers will be obtained. We hypothesize that tumors that do not demonstrate the changes that correlate with response after cetuximab in the *in vivo* preclinical studies are more likely to progress following cetuximab-radiation therapy compared to those that show changes that correlate with response. If our hypothesis is validated, we will gain a tool that will help identify patients who are most likely to benefit from radiation and cetuximab, a very expensive and moderately toxic treatment.

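### Sections 1.1 and 21.1 seek a marker change that predicts outcome, but the plan only relates marker to outcome and never measures how well a marker separates patients

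*Combined protocol and SAP*

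**What the plan says.** The aim is stated as prediction. Section 21.1 wants "to determine if biomarker response to a loading dose of cetuximab is predictive of that outcome". Section 1.1 goes further: "We also propose to develop a molecular pharmacodynamic predictor of local control after treatment with combination cetuximab-radiation". It adds that, if the hypothesis is validated, the result would help to identify the patients most likely to benefit. Section 21.4 justifies the design partly by the value of a screen for such patients.

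The analysis is stated as association. Under section 21.3.2, logistic and Cox "regression will be used to relate clinical out (local recurrence, progression-free survival or overall survival) to changes in markers across the loading dose". On which markers, the same section says "All of the markers will be analyzed, but markers that are modulated by the loading dose" will be of particular interest. The formal objective in section 2.1.2 is to correlate outcomes with marker changes.

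The sample size rests on a single-marker Cox test. Section 21.4 takes as effect size the "difference between the mean of the marker for patients with PFS less than the median" minus the mean for the remaining patients, in SD units, and reports that "the power to reject the null hypothesis of no effect is at least 80% if the effect size is 1.1 standard units or greater".

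Neither section 21 nor the analysis text of Appendix B names a concordance index, ROC area, sensitivity, specificity, cut-point, internal validation or minimum performance.

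**The concern.** A coefficient that differs from zero shows that marker and outcome are related. It does not show that the marker sorts patients well enough to serve as a tool or screen. A reader given a hazard ratio and p-value from this trial could not tell whether the marker separates patients strongly or only a little better than chance.

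The gap would exist with one pre-named marker that truly relates to outcome, so it is separate from the number of markers tested. At stake is whether the trial can answer the question in section 21.1, and how far a marker reported from 50 patients can be trusted when a follow-on study is considered.

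**Working it through.** **Inputs from section 21.4.** 50 patients; accrual over 36 months; analysis 6 months after the last patient is treated; median 22 months; normally distributed marker; alpha 0.05.

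**Assumptions added.** Two-sided test (sidedness is not stated), exponential event times, uniform accrual, and a marker with SD 1 within each group, shifted by d for patients whose PFS is below the median.

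**Step 1: expected events.** The hazard is ln 2 / 22 = 0.0315 per month, and potential follow-up is uniform from 6 to 42 months. The expected event fraction is 1 − [exp(−6 × 0.0315) − exp(−42 × 0.0315)] / (36 × 0.0315) = 1 − (0.828 − 0.266) / 1.134 = 0.505. Times 50, this is about 25 events.

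**Step 2: reproduce the plan's figure.** Simulating the one-covariate Cox test gives power of 77–78% at 1.0 SD, 81% at 1.05 SD and 84–85% at 1.1 SD. The statement of at least 80% power at 1.1 SD reproduces.

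**Step 3: what a just-significant result looks like.** As an approximation, the boundary hazard ratio per SD is exp(1.96 / √25.3) = 1.48. Simulated results near z = 1.96 give about 1.5, with an apparent C-index of about 0.62.

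**Step 4: translate to separation of patients.** With the outcome split at median PFS and the marker cut midway between the two group means, sensitivity and specificity both equal Φ(d/2), and the misclassified fraction is Φ(−d/2). In the section 21.4 model, a mean log hazard ratio of 0.41 (hazard ratio 1.5) and power of about 50% both occur near d = 0.7. The boundary result therefore corresponds to about 0.7 SD.

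| True effect d (SD) | Power | Misclassified, Φ(−d/2) |
|---|---|---|
| 0.5 | about 29% | 40% |
| 0.7 | about 49% | 36% |
| 1.1 (design effect) | about 84% | 29% |

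**Step 5: inflation among significant results.** At d = 0.5 the mean log hazard ratio per SD is 0.30 over all simulated trials and 0.55 over the significant ones: 0.55 / 0.30 = 1.8. At d = 1.1 the corresponding ratio is 1.09.

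**Step 6: optimism in the C-index.** For one pre-named marker in a one-covariate model, only the sign of the coefficient is learned from the data. Simulated bootstrap optimism is 0.017 at d = 0.5 and 0.004 at d = 1.1. It becomes a material issue when a marker is selected from several.

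**The case against.** The strongest reply is that the plan does more than test a null hypothesis. Section 21.3.2 speaks of relating outcome to marker change, its models also yield hazard and odds ratios, and the explicit test of no effect for this objective belongs to the sizing argument in section 21.4. The hypothesis in section 1.1, that tumours lacking the expected changes are more likely to progress, is comparative, and regression addresses it. This stands, but a hazard ratio of 1.5 per SD does not tell a reader how well patients are separated. Nor is the analysis labelled exploratory, as the toxicity modelling and HPV analyses are: it is Primary Objective 2 and the basis of the sample size.

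Three stronger readings are tempting and not supported:

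- **That the plan will call any significant marker predictive, or carry it forward on p < 0.05.** No section contains such a rule.
- **That a marker misclassifying 40% of patients passes.** It can pass, but under the section 21.4 model it fails in about 71% of trials. Estimates of 39–40% at the significance boundary come from other models (a two-sample t-test analogue and a proportional-hazards marker).
- **That 1.8-fold inflation is typical.** It applies to an effect less than half the one the trial was sized for.

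Precision also limits what can be asked. Under the section 21.4 timing, patients accrued in the last 16 of 36 months (44%) have less than 22 months of potential follow-up, and about 29% would have unknown status at 22 months. With 25 patients in a group, a sensitivity of 15/25 has an exact 95% CI of 39% to 79%. Sensitivity and specificity are therefore a poor choice as a required standard here.

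**Conclusion.** The concern holds as a mismatch between aim and planned evidence. The documents aim at a predictor and plan only association, with no measure of discrimination. At the edge of significance the C-index is about 0.62 and about 36% of patients are misclassified. Even at the effect the trial was sized for, 29% are misclassified.

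The misclassification figures are derived and do not appear in the documents. They rest on a normal marker, a midpoint cut, outcome split at median PFS and two-sided testing. The mismatch itself depends on none of these.

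This is a gap in reporting and interpretation. The power statement reproduces, and nothing here invalidates the regression analyses.

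**What to change.** In section 21.3.2:

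- Report for each marker the C-index for PFS with a 95% CI, alongside the hazard ratio.
- Wherever a marker is chosen from several, add a bootstrap optimism correction that repeats the selection step in each resample.
- State that a significant coefficient on its own shows association.
- Optionally add sensitivity and specificity at a fixed time, with CIs, as descriptive figures only.

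The cost is a little more analysis on data already collected, with no additional patients, biopsies or visits. The drawback is that the figures will be imprecise with 50 patients and about 25 events, and will look less favourable than a p-value.

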## 9.0 Measurement of Response

### 9.4 Tumor Clearance

A primary clinical endpoint of this study is progression-free survival. A patient will be considered to have a complete response if there is no measurable or palpable tumor either on clinical or radiographic (CT-PET scan or MRI) examination assessed within approximately 3 months after the completion of treatment. Complete response will

be defined as complete disappearance of disease (in which case 9.2 will apply to assess relapse) or residual radiographic abnormality (which cannot be safely biopsied) that is not considered to be tumor (in which case section 9.3 will apply to assess progression).

**9.5**                    Local or Regional Relapse

Relapse is defined as reappearance of tumor after complete response. If possible, relapse should be confirmed by biopsy.

**9.6**                    Local or Regional Progression

Progression is defined as an estimated increase in the size of the tumor (product of the perpendicular diameters of the two largest dimensions) of greater than 25%, taking as reference the smallest value of all previous measurements or appearance of new areas of malignant disease.

**9.7**                    Distant Metastasis

Clear evidence of distant metastases (lung, bone, brain, etc.); biopsy is recommended where possible. A solitary, spiculated lung mass/nodule is considered a second primary neoplasm unless proven otherwise.

**9.8**                    Second Primary Neoplasm

Tumor reappearing with the initial and immediate adjoining anatomical region of the primary will be considered local recurrence. Multiple lung nodules/masses are considered distant metastases from the index cancer unless proven otherwise.

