**10.0**                **Criteria for Discontinuation of Treatment**

In the absence of treatment delays due to adverse events, treatment may continue through completion of concurrent chemoradiotherapy and consolidation chemotherapy or until one of the following criteria applies:

- Local-regional disease progression
- Intercurrent illness that prevents further administration of treatment
- Unacceptable adverse events(s)
- Patient decides to withdraw from the study
- General or specific changes in the patient's condition render the patient unacceptable for further treatment in the judgment of the investigator.

If treatment is interrupted due to a non-dose-limiting adverse event or any reason other than toxicity, such as a holiday, bad weather, or a transportation problem, the duration of therapy will be extended accordingly. If a patient misses a day of radiation and chemotherapy, then the weekly chemotherapy should be delivered the next day and the missed radiation fraction will be given after the completion of planned treatments.

Patients who exhibit local-regional tumor progression will discontinue all study procedures and will be medically managed. For the purposes of the research, they will continue to be followed for toxicity and survival. These patients may be treated with other agents.

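### Section 21.2 treats patients who stop cetuximab+RT for progression, or who die on treatment of a non-toxic cause, as unevaluable and replaces them; the PFS and OS summaries then depend on early outcome

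*Combined protocol and SAP*

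**What the plan says.** Section 21.2 plans fifty evaluable patients. To be evaluable for the primary objectives a patient must have Research Biopsies #1 and #2 and must be one who "either completes the full course of cetuximab+RT or has cetuximab+RT stopped for toxicity. Unevaluable patients will be replaced".

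The same rule covers all three primary objectives. The second is to "Characterize clinical outcomes, including local recurrence, progression-free survival and overall survival in these patients" and to correlate those outcomes with marker changes. Clinical outcome is a stated aim in three other places:

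- Section 1.1: "The primary end-point of this trial is to characterize local progression free survival in these patients, when treated with cetuximab+radiation".
- Section 9.4: "A primary clinical endpoint of this study is progression-free survival".
- Section 21.1: the study is a "single-arm, Phase II trial to characterize the clinical outcome of standard of care".

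Section 10.0 gives five reasons to stop treatment. Local-regional progression, intercurrent illness, patient withdrawal and a change in condition are each listed apart from unacceptable adverse events. On progressors it says: "Patients who exhibit local-regional tumor progression will discontinue all study procedures and will be medically managed". It adds that for research purposes "they will continue to be followed for toxicity and survival".

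Sections 21.3 and 21.4 name no all-treated set and no sensitivity analysis on a wider set.

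**The concern.** A patient who stops for progression has neither completed the course nor stopped for toxicity. The same is true of a patient who dies during treatment of a cause unrelated to it. Under 21.2 both are unevaluable, and each is replaced by someone who got through the same weeks or stopped for toxicity. Whether a patient is analysed then depends partly on the outcome being estimated.

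The trial has one arm, so no comparator offsets the selection. The population was chosen for age, poor performance status or comorbidity, and section 21.4 says outcomes of this therapy have not been systematically studied. The descriptive PFS and OS figures are therefore a main product of the trial. A bias of this kind does not shrink as patients are added.

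**Working it through.** **1. The plan's own figure.** Section 21.4 gives at least 80% power at a marker effect of 1.1 standard units. The simulation used 50 patients, uniform accrual over 36 months, analysis at month 42, exponential PFS with a 22-month median, a two-sided test at 0.05 and the standard deviation taken within group. It gives 83.6% (Wald) or 84.3% (likelihood ratio), with about 25 events. The stated power is reproduced and is not in question.

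**2. Inputs for the effect on PFS.**
- Median 22 months (21.4): λ = ln 2 / 22 = 0.0315 per month.
- Treatment window from the loading dose. Biopsy #2 is at day 7 ± 1 and RT starts within about 4 days (7.1). RT lasts about 7-8 weeks (12.11). Shortest: 7 + 49 = 56 days. Longest: 7 + 1 + 4 + 56 = 68 days. That is t0 = 1.84 to 2.23 months, with 63 days as midpoint.
- Assumptions not in the documents: constant hazard, time counted from the loading dose, and f, the fraction of on-treatment events that lead to exclusion.

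**3. Formulas.** Probability of an event in the window: p = 1 − exp(−λ·t0) = 5.6% (56 days), 6.3% (63 days), 6.8% (68 days). After t0, PFS among retained patients is exp(−λt) / (1 − f·p). The retained median is 22 − ln(1 − f·p)/λ. Patients treated per 50 retained: 50 / (1 − f·p).

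**4. Results for 56 to 68 days.** Without exclusion the median is 22.0 months and 12-month PFS is exp(−12λ) = 68.5%.

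| f | Treated per 50 retained | Median PFS, months | 12-month PFS | Shift |
|---|---|---|---|---|
| 0.25 | 50.7-50.9 | 22.45-22.54 | 69.5-69.7% | +0.5 months; +1.0 to +1.2 points |
| 0.5 | 51.4-51.8 | 22.91-23.10 | 70.5-70.9% | +0.9 to +1.1 months; +2.0 to +2.4 points |
| 1 | 53.0-53.7 | 23.84-24.23 | 72.6-73.5% | +1.8 to +2.2 months; +4.1 to +5.0 points |

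Standard error of 12-month PFS at n=50, ignoring censoring: √(0.685 × 0.315 / 50) = 6.6 points.

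**5. If the early hazard is higher.** Double the hazard during a 63-day window and keep λ afterwards. Survival to t0 is exp(−2 × 0.0315 × 2.07) = 0.878. All-treated 12-month PFS is 0.878 × exp(−0.0315 × 9.93) = 64.2%. With every early event removed it is 64.2 / 0.878 = 73.1%, a shift of +8.9 points. If the later hazard is instead reset so that the median stays at 22 months, the shift is +9.2 points.

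**6. Marker Cox analysis.** There were 4,000 simulations per case, n=50 after replacement, with a cut-off of 63 days and an assumed log-HR of −0.6 per SD.

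| f | Mean log-HR | Events | Power |
|---|---|---|---|
| 0 | −0.625 | 25.0 | 81% |
| 0.25 | −0.626 | 24.6 | 79% |
| 0.5 | −0.634 | 24.1 | 79% |
| 1 | −0.620 | 23.3 | 76% |

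Type I error at f = 0, 0.5 and 1 is 5.2%, 4.8% and 5.0%. A log-HR of −0.6 corresponds to about 0.74-0.80 SD in the plan's metric, so this check is not calibrated to the plan's 1.1.

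**7. Local recurrence.** Section 9.5 says: "Relapse is defined as reappearance of tumor after complete response". Suppose 53 patients are treated, 3 on-treatment progressors are removed, and r patients relapse later. If only relapse counts, r/53 becomes r/50, a relative rise of 53/50 − 1 = 6%. If on-treatment progression also counts, (r+3)/53 becomes r/50, a fall for every r below 50. The direction depends on a definition that the plan does not give.

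**The case against.** The best reply is that 21.2 is headed as a rule on patient numbers. It governs accrual, and 21.3 never says that outcome summaries are confined to evaluable patients. Section 10.0 keeps progressors in follow-up for research purposes, which suggests that their outcomes were meant to be used. This stands in part. A reader might infer that the sponsor decided to delete early failures, and the documents do not show that. They show a rule that ties evaluability to the primary objectives, with no other set named. Followed as written, it removes these patients.

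A second reply is that little hangs on it. Section 21.4 has no stopping rule for efficacy or toxicity, no PFS threshold is set, and 21.3.2 names only logistic and Cox regressions on markers. It is true that no decision turns on the estimate. But characterising outcome is a stated primary aim, so the descriptive figures still matter.

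A third reply is that the size is conjecture. That is right. Section 8.0 schedules no imaging during RT, with formal restaging 12-14 weeks afterwards, so few progressions may be recorded on treatment. Equally, early failure could be more frequent than a constant hazard implies in a frail group.

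Finally, requiring two biopsies is reasonable for the marker objectives. The completion-or-toxicity condition is the part that does not belong there, or in the clinical outcomes.

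**Conclusion.** The concern holds as a fault in the analysis set. Removing on-treatment progressions biases PFS upward. Removing on-treatment deaths biases OS upward. It biases PFS upward too if death is a PFS event, but section 9 does not define PFS, and section 1.1 speaks of local PFS, for which death without local progression may not count.

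Under constant hazard and the plan's 22-month median, the shift runs from 0.5 to 2.2 months in the median and from 1.0 to 5.0 points at 12 months, below one standard error.

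Stronger readings that the documents do not support:

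- That 5.0 points is an upper limit, or that the shift is surely within sampling error. A doubled on-treatment hazard gives about 9 points against a standard error of 6.6.
- That OS is certainly inflated overall. For removed progressors this assumes shorter survival. The net effect of also removing withdrawals and non-fatal intercurrent illness is unknown.
- That the toxicity rate or local recurrence moves in a known direction.
- That the marker analysis is invalid. At the assumed effect it shows no material bias and loses at most about 2 of 25 events.

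The point is worth fixing because it touches a primary aim and the remedy is cheap.

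**What to change.** Add analysis-set definitions to section 21:

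- **Clinical outcomes and toxicity:** all patients who received any cetuximab, regardless of completion or reason for stopping. Report the evaluable set, or those who started RT, as a sensitivity analysis. The latter meets the argument that section 1.1 concerns patients treated with both modalities.
- **Marker analyses:** all patients with paired biopsies, including those who progress or die on treatment. Say how early withdrawals are handled.
- **Replacement:** may continue until 50 patients have paired biopsies, but replaced patients stay in the clinical-outcome and toxicity sets.
- **Definitions needed to apply this:** which events count for PFS (in particular death), its time origin, and whether on-treatment progression counts as local recurrence.

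The cost is mostly wording. Section 10.0 already follows progressors for toxicity and survival, section 8.0 plans disease-status and survival follow-up, and section 17.0 collects adverse events from the first dose. There is some extra work: the section 8.0 follow-up visits are timed from the end of RT, so patients who stop early without progression need their disease status recorded from routine follow-up, or are censored at last assessment. Reported PFS and OS are likely to be slightly less favourable.
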